1.0 Background & Rationale

EIB is a multifactorial condition characterized by airway inflammation, hyperresponsiveness, and airway narrowing following a bout of exercise in those with and without previous asthma diagnosis (1-9). Common techniques used to invoke bronchoconstriction and diagnose EIB are exercise and eucapnic voluntary hyperpnea (EVH). EVH is the method recommended by the International Olympic Committee to diagnose EIB in athletes (4, 10-12). Positive EIB diagnosis is defined as a $\geq 10\%$ drop in forced expiratory volume in 1 second (FEV₁) after an EVH challenge compared to baseline (4, 8, 9). The severity of EIB can be classified in the following manner: Mild EIB is characterized as $\geq 10\%$ drop in post-EVH FEV₁, moderate is a $\geq 25\%$ drop in post-EVH FEV₁, and severe EIB is a $\geq 50\%$ drop in post-EVH FEV₁, according to the American Thoracic Society Guidelines (4, 8, 13).

Elite athlete populations appear to have a high prevalence of EIB ranging from 10 to 60% for EIB and 17% for asthma, particularly in endurance sports such as running, cycling, rowing, and swimming (1, 2, 4, 7, 9, 11, 14). Carlsen et al., (2) reported 67 out of 597 American Olympic athletes in the 1984 Los Angeles summer Olympic Games had asthma or exercise-induced asthma. In the 1996 Olympics, asthma prevalence in cyclists and mountain bikers was 45%, while EIB was not documented in weightlifters and divers. EIB-positive athletes commonly experience symptoms such as wheezing, coughing, shortness of breath, dyspnea, and chest tightness during or after exercise (1, 4, 6, 15-17). Symptoms may last up to a few minutes or hours post-exercise but are reversible and manageable with medication (1-9). The mechanisms postulated to cause EIB are airway dehydration and high ventilation rates during exercise, leading to increased airway dryness and airway osmolarity, and a subsequent release of inflammatory mediators from airway cells, such as leukotrienes, prostaglandins, and histamine (1, 2, 4, 6-8). These inflammatory mediators can subsequently cause edema, constriction of airway smooth muscle, and increased mucus production (1, 2, 4, 6-8).

Treatment options for EIB heavily include pharmacological strategies, while non-pharmacological strategies are scarce. The most common pharmacological treatments are short-acting β_2 -agonists (SABA) (1, 4, 6, 8, 9, 15, 18, 19). SABAs stimulate airway β_2 -receptors causing relaxation of smooth muscle, and thereby dilating the airways. Inhaled forms like salbutamol or albuterol are commonly prescribed and taken 5-20 minutes before exercise (1, 4, 6, 8, 9). However, frequent use of SABAs may result in medication tolerance leading to a reduced efficacy in attenuating bronchoconstriction (1, 4, 8). There is emerging evidence that non-pharmacological therapies may be used to supplement traditional therapies to reduce the severity of EIB and minimize exercise respiratory symptoms (1, 4, 6, 8, 9, 15, 18-21). One of these non-pharmacological interventions that is the most available and cost-effective is inspiratory muscle training (IMT) (1-9, 22). This technique aims to increase the strength and endurance of the diaphragm and accessory muscles of respiration. Flow-resistive IMT typically consists of taking voluntary inspirations against a resistive load across an entire range of vital capacity while at rest (11, 23-32). This loading protocol requires the athlete to breathe through a 2mm diameter orifice in the device, which increases the pressure required to produce a given airflow (26, 29, 30, 33-35). IMT is typically performed in a laboratory or at home with an IMT device several times a week for 6 to 12 weeks (26, 29, 30, 33-35).

In healthy individuals, the most notable effects of IMT are an increase in diaphragm thickness and strength, a decrease in exertional dyspnea, and a decrease in respiratory and limb locomotor muscle deoxygenation during exercise (20, 23-27, 29, 36-42). The use of IMT

in asthma has been shown to improve inspiratory muscle strength, reduce dyspnea, medication use, and asthma symptoms (11, 17, 23-27, 29-32). Importantly, Turner et al., (31) has shown that pressure threshold IMT improved exercise tolerance by 16% and reduced the perception of dyspnea by 16% during cycling exercise performed at $\sim 70\%$ $\text{VO}_{2\text{max}}$ until exhaustion. Following IMT, inspiratory muscle strength and endurance increased 28% and 16%, respectively, and VO_2 decreased by 6% at minute 4 and 12% at the end of a constant load cycling exercise. It was speculated that the decrease in dyspnea perception might be due to increased inspiratory muscle strength, while the reduced VO_2 observed during constant load cycling exercise following IMT may be related to changes in strength and/or operating lung volumes during exercise (31).

Weiner et al., (43) found a proportional correlation between perception of dyspnea and β_2 -agonist use in individuals with mild to moderate asthma (44). Thus, decreased β_2 -agonist use decreased perception of dyspnea (Borg scale). In support, Weiner et al., (45) found individuals with mild asthma improved their inspiratory muscle strength, which was associated with a decrease in the modified Borg scale for dyspnea perception during a resistive breathing test. Furthermore, β_2 -agonist use decreased in the high β_2 -agonist user group in the last four weeks of training. Duruturk et al., (46) found that respiratory muscle strength, measured by maximal inspiratory pressure (MIP), increased after IMT in asthmatics. In addition, distance walked in a 6-minute test was improved, fatigue decreased, and dyspnea score decreased in the IMT group.

EIB may result in decreased exercise tolerance and performance, dynamic hyperinflation (DH), and decreased inspiratory muscle strength, leading to the onset of exertional dyspnea (ED) (19). ED is defined as the perception of the intensity and difficulty of breathing (15, 18, 19, 47-50). Common mechanisms leading to ED are chest tightness and work or effort of breathing (47). Work or effort of breathing has been theorized to be related to the respiratory system's central and peripheral coupling of muscle tone regulation, while chest tightness represents the degree of bronchoconstriction (15, 19, 47). The underlying mechanism responsible for ED is thought to involve dynamic hyperinflation (DH) of the lungs. DH occurs when there is a progressive increase in end-expiratory lung volume (EELV) during exercise with bronchoconstriction due to air trapping. This increase in EELV constrains tidal volume (V_T) closer to total lung capacity and the steeper, non-compliant region of the pressure-volume relationship between the lung and chest wall where elastic loading is greater to overcome (19, 32, 36, 37, 50-52). When there is a decrease between the volume of air to exhale, complete exhalation time, and frequency of inspirations, EELV increases (19, 32, 36, 37, 51), resulting in the immoderate elastic stretch of the inspiratory muscles forcing the muscles to function outside their optimal scope (15, 19, 49). The muscles then become weak, which results in a greater perception of dyspnea with the additional respiratory muscle work needed to overcome elastic loading forces (15, 19).

If EIB is not diagnosed and treated, a decrease in an athlete's performance may be detrimental to their athletic success. The athlete may have exacerbated symptoms, such as wheezing, increased mucus production, and coughing during exercise and excessive fatigue post-exercise. Due to leftward shifts in the pressure-volume curve with dynamic hyperinflation, respiratory muscle work increases, and respiratory muscle fatigue sets in (1-5, 9, 16, 18, 23, 26, 35, 53). Repeated mechanical contraction and resulting metabolites (e.g. hydrogen ions, potassium ions, bradykinin, phosphate, and prostaglandins) produced by fatiguing respiratory muscles stimulates signals from the group III/IV phrenic nerve afferents. This enhances sympathetic efferent signals to limb skeletal muscles, resulting in a redirection of blood flow from the lower limb muscles to the respiratory muscles – a phenomenon termed respiratory

muscle metaboreflex (9, 18). Therefore, respiratory muscle oxygen uptake increases at the expense of decreased locomotor oxygen uptake. In response, the locomotor skeletal muscles' metaboreceptors send afferent signals to the brain (also known as the central governor), increasing the sensation of fatigue, and decreased motor unit drive to the limb locomotor muscles, resulting in exercise performance decrement (5, 9, 18, 26, 32, 35, 44, 47, 53-55).

It has been postulated that EIB may be exacerbated by exercise. Price et al., (9) described that airflow limitation due to increasing exercise ventilation rates might cause airway stress, dynamic hyperinflation, and decreased respiratory muscle efficiency (1-9). The resultant ventilation-perfusion mismatch may reduce alveolar gas exchange. Therefore, this change in oxygen kinetics and an increase in an athlete's perception of effort and symptoms, due to dynamic hyperinflation and airway stress, may result in reduced exercise capacity (1-5, 9, 16, 18, 23, 26, 35).

To our knowledge, no study has been conducted assessing the impact of IMT on EIB severity, ED, and cycling time-trial performance. A review by Shei et al., (30) noted that studies examining the impact of IMT on asthma have all demonstrated an increase in inspiratory muscle strength (maximal inspiratory pressure, MIP) and endurance (sustained maximal inspiratory pressure). In addition, it has been observed that the reduction in the perception of dyspnea following and during exercise leads to a reduction in SABA use and fewer asthma symptoms (30, 43-45). Shei et al., (30) also noted the lack of data available to explain the impacts of IMT on exercise performance and tolerance in athletes with EIB. Interestingly, Price et al., (9) suggested that more prolonged duration exercise with specific aerobic demands could provoke airway obstruction and hinder performance.

Due to the lack of studies examining the impact of IMT on the severity of EIB and exercise performance, the specific aim of this study is to assess the efficacy of flow-resistive IMT on EIB severity and symptoms, SABA medication use, operating lung volumes, respiratory and limb locomotor muscle deoxygenation during constant-load cycling exercise, femoral blood flow, exertional dyspnea, and cycling time-trial performance. It is hypothesized that eight weeks of IMT will reduce EIB's severity and symptoms, respiratory and limb locomotor muscle deoxygenation, improve operating lung volumes, and exertional dyspnea and improve cycling time-trial performance.

2.0 Objective(s)

2.1 Primary Objective

Aim 1a. To examine the effect of flow-resistive inspiratory muscle training on the severity of exercise-induced bronchoconstriction (EIB) after inspiratory muscle training (IMT). More specifically, the pre- and post-values of the percentage drop in forced expiratory volume in 1 second (FEV₁) from the eucapnic voluntary hyperpnea (EVH) test before and after IMT will be measured.

We hypothesize IMT will reduce the severity of EIB. We anticipate there will be differences in the percentage drop in FEV₁ after EVH testing, resulting in a lessening of EIB severity.

Aim 1b. To examine the effects of flow-resistive inspiratory muscle training on the strength and endurance of the inspiratory muscles. More specifically, the pre-

to post-values of maximum inspiratory pressure and sustained maximum inspiratory pressure before and after IMT will be measured.

We hypothesize IMT will increase the maximum inspiratory pressure and sustained maximum inspiratory pressure post-training. We anticipate there will be differences in the MIP and SMIP values, resulting in the improvement of inspiratory muscle strength and endurance.

Aim 1c. Evaluate differences in constant load parameters and 16-km cycling time-trial completion time and power output before and after IMT.

We hypothesize power output will increase during constant load cycling after training. In addition, subjects time-trial time performance will improve and power output will increase after IMT.

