3.0 Outcome Measures

3.1 Primary Outcome Measures

Outcomes of interest is the severity of exercise-induced bronchoconstriction (EIB), inspiratory muscle strength and endurance, and cycling performance.

EIB severity will be measured using the pre- and post-values of the percentage drop in forced expiratory volume in 1 second (FEV₁) obtained from the eucapnic voluntary hyperpnea (EVH) test before and after IMT.

Inspiratory muscle strength and endurance will be measured using the flow-resistive trainer device that will record maximum inspiratory pressure and sustained maximum inspiratory pressure for 8 weeks.

Cycling performance will be summarized by pre- to post-values in power output, time, and speed time to complete the time-trial and constant loads before and after IMT.

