5.0 Study Design

The study design is a randomized, single-blind parallel group study. Participants will complete a formal screening visit and five experimental visits. The five experimental visits will occur each day ± 1 hour, at least 24 hours apart, and ≥ 2 hours postprandial.

The participants were required to visit the laboratory 5 times to complete the experimental tests. *Visit 1.* Participants underwent pulmonary function testing (PFT) and completed a eucapnic voluntary hyperpnea (EVH) challenge to diagnose EIB. *Visit 2.* Participants completed an incremental cycle ergometer test to determine VO_{2peak}. Male participants began with a 3-minute warm-up at 60W (61). After the warm-up, the test started at 100W and increased by 30W every minute until exhaustion (33, 61). A participant's VO_{2peak} was determined as the highest 30-second average VO₂ value (33, 61). All participants had a 1-hour rest period before the 16-km familiarization time-trial. *Visit 3.* Each participant completed two 8-minute constant-load exercise bouts, one at moderate intensity and another at submaximal intensity, and had a 1-hour rest period before the 16-km time-trial. After visit 3, participants were randomly assigned to either an IMT or a sham-IMT (control) group using a random number generator (1 = IMT, 2 = sham-IMT). Participants used a flow-resistive inspiratory muscle trainer (Pro2Fit, Smithfield, Rhode Island) in order to complete eight weeks of IMT, performed three times a week, prior to any exercise training that day. After 8 weeks of the IMT or Sham-IMT intervention, participants returned to the laboratory to repeat the PFTs, the EIB diagnosis via EVH, the familiarization time-trial, and the constant-load and performance time-trial post-IMT for *Visit 4* and *Visit 5*.

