Constant Load & Time-Trial Cycling Exercise: Before exercise, the participant adjusted the seat height on the cycle ergometer (Velotron, Velotron® Racermate, Seattle, WA), and then were fitted with a facemask (Hans-Rudolph, Shawnee, KS) and flow probe connected to a metabolic cart (Vmax® Encore, Vyair Medical, Mettawa, IL) and a Polar HR Monitor (Polar, Helsinki, Finland) underneath the sternum. Each participant completed two constant-load (CL) exercises with a 5-minute rest period in between, one at 15% below the gas exchange threshold (GET; CL1) and another at 15% above the gas exchange threshold (CL2), corresponding to 85% $\text{VO}_{2\text{peak}}$ (42). Males warmed up for 5 minutes at 60W, followed by a 5-minute rest (42, 66). After the 5-minute rest period, participants cycled at 5W for 2 minutes, immediately followed by a predetermined moderate workload. The moderate and submaximal workloads are determined from their GETs, estimated from changes in breath values using the modified V-slope method (42). Each participant completed a familiarization time-trial (TT) to learn the cycle gearing system and to reduce any further learning effects (61, 67). The cycle ergometer recorded each participant's power output (PO), speed, and time to complete the time-trial (33). The ergometer allows participants to vary their resistance and power output, with an electronic gearing system during the 16-km TTs, simulating an actual performance scenario.

Ratings of exertional dyspnea & leg fatigue: During constant-load cycling and the cycling time-trial, three modified Borg scales (0-10) were placed at arm's length, comfortably reachable by the participant on the cycle ergometer. Participants were asked to indicate their ratings of perceived breathing intensity, 0 indicating "not noticeable" and 10 indicating "maximal intensity imaginable". Secondly, participants were asked to rate perceived breathing unpleasantness, with 0 indicating "not unpleasant" and 10 indicating "maximal unpleasantness imaginable". Lastly, participants were asked to rate leg fatigue, with 0 indicating "not fatigued at all" and 10 indicating "total fatigue and exhaustion". Ratings were recorded every 2 minutes during each of the 8-minute constant loads and every 4 km during the 16-km time-trial.

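### Constant-load power is a primary performance outcome, but the laboratory prescribes it, so it cannot show a response to training

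*Combined protocol and SAP*

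**What the plan says.** Section 2.1, Aim 1c, is a primary objective. Its scope is "Evaluate differences in constant load parameters and 16-km cycling time-trial completion time and power output before and after IMT", and its hypothesis for the constant loads is "We hypothesize power output will increase during constant load cycling after training". The constant-load parameters are not defined further.

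Section 3.1 carries this into the primary outcomes: "Cycling performance will be summarized by pre- to post-values in power output, time, and speed time to complete the time-trial and constant loads".

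The procedures describe the bouts differently:

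- **Duration.** Section 5.0: "Each participant completed two 8-minute constant-load exercise bouts". Section 6.0 agrees: "Ratings were recorded every 2 minutes during each of the 8-minute constant loads".
- **Load.** Section 6.0: "participants cycled at 5W for 2 minutes, immediately followed by a predetermined moderate workload". Both loads come from the participant's gas exchange threshold (GET), CL1 at 15% below it and CL2 at 15% above.
- **Timing of the threshold test.** Section 5.0 places the incremental test at Visit 2. It is not among the tests repeated at Visits 4 and 5.
- **Free choice of power.** Section 6.0 describes this, through the electronic gearing, for the 16-km time-trials only.

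Section 8.0 applies a time-by-group ANOVA to every outcome variable and treats the interaction as the main test of efficacy.

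**The concern.** An outcome can show a treatment effect only if the participant's response is free to move it. In a constant-load bout the laboratory chooses the load and the participant rides it. What responds is physiology and perception: breathlessness, leg fatigue, deoxygenation, blood flow and lung volumes. Calling the load itself a primary performance result confuses the prescription with the response.

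One component of one of the three primary domains is therefore not interpretable. The standard analysis would return either no result or a change made by whoever set the ergometer. A reported rise in constant-load watts could be taken for a training benefit. It would also mean that the secondary constant-load measures were compared at different loads before and after training.

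**Working it through.** This is a check of design logic. The plan gives no figure for this outcome to reproduce. The planned sample size of 20 plays no part, because the conclusion holds at any number of participants.

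**Inputs.** The 8-minute duration is from Sections 5.0 and 6.0. The pre-set, GET-based load is from Section 6.0. The list of repeated tests is from Section 5.0. The 2 × 2 ANOVA with interaction, the planned 10 per group and the 11 completers are from Section 8.0. The split of the 11 is not given, so 6 v 5 is assumed for illustration.

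**Equivalent test.** With two time points and two groups, the interaction test is the two-sample test of change scores. With d = post − pre,

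t = (mean d in IMT − mean d in sham) / SE, and F = t².

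**Case A: same watts before and after.** Let W be a participant's prescribed load.

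- d = W − W = 0 for everyone, in both groups.
- Numerator = 0 − 0 = 0. All changes are identical, so their SD is 0 and SE = 0.
- t = 0/0. Run on zeros, the test returns no statistic and no p-value for 10 v 10 (18 degrees of freedom) and for the assumed 6 v 5 (9 degrees of freedom).

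Any non-zero change in this case could come only from recording noise or an incomplete bout.

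**Case B: watts re-set after training.** Assume the 15% applies to the power at GET, written G.

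- CL1: d = 0.85 × (G post − G pre).
- CL2: d = 1.15 × (G post − G pre).

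The change is a rescaled change in threshold, entered by the laboratory. It says nothing about what the participant achieved in the bout, and no post-training test that would supply G is described.

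**Time.** Let T be minutes ridden, so T ≤ 8 at each visit. A participant who completed the bout before training has d = T post − 8 ≤ 0, so no improvement can be recorded. Only someone who stopped early before training could show a gain. No early-stop endpoint is defined, and Section 7.0 lists inability to complete the exercise tests as a possible reason for withdrawal.

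**Speed.** The documents do not show that speed is fixed during the constant loads. Nor do they say how speed at a set load would express performance. Section 6.0 describes the ergometer's recording of power, speed and time in connection with the time-trial.

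**Contrast.** In the 16-km time-trial the distance is fixed and the participant chooses the power, so completion time and power are both free to vary.

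**The case against.** The strongest reply is that no sentence says the Visit 2 watts were reused. That stands: reuse is inferred from the absence of an incremental test at Visits 4 and 5. A reader might infer a documented change of exactly 0 in both arms, and the text does not support that. The conclusion survives because Case B does not measure performance either.

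Second, time could fall short of 8 minutes, so its change need not be zero. This also stands. Time is capped, not constant.

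Third, the Aim 1c hypothesis names only power for the constant loads. Constant-load time and speed enter through Section 3.1 alone, in a sentence whose wording is unclear. The undefined parameters in Aim 1c could have been meant as physiological responses. That is possible, but the hypothesis names power output and Section 3.1 names power, time and speed.

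Fourth, Section 8.0 calls the findings preliminary and does not read non-significance as absence of effect. This limits the harm. A reader might also infer that the test would be reported as a failed primary hypothesis, or that its power merely cannot exceed alpha. Neither description fits Case A, where the statistic is undefined and there is no p-value to misread.

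Finally, removing a primary quantity after participants have completed is a change of outcome, not mere editing. That is right, and it determines how the fix must be made.

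**Conclusion.** The concern holds for constant-load power. As the procedures are written, it is prescribed and cannot measure a response to training. The time-by-group test is undefined if the watts were unchanged, and it reflects the prescription if they were re-set. No sample size repairs either case. Constant-load time is an unsuitable performance measure because it is capped at 8 minutes with no exhaustion endpoint. Constant-load speed has no stated meaning as performance, though it is not shown to be fixed.

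The conclusion rests on the bouts having been run as Sections 5.0 and 6.0 describe. It does not require the assumption that the watts were identical.

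A reader might infer that Aim 1c as a whole, or the whole cycling outcome, is untestable. The documents do not support that. Time-trial completion time and power are free to vary, and the other primary outcomes (percentage fall in FEV₁, and inspiratory muscle strength and endurance) are untouched. The secondary responses during the constant loads can still be measured. The background in Section 1.0 points the same way: it names time-trial performance as the cycling performance target and does not hypothesize a rise in constant-load power.

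**What to change.** 1. Remove the constant-load power hypothesis from Aim 1c.
2. Remove constant-load power, time and speed from the primary cycling performance outcome in Section 3.1. Keep the 16-km time-trial completion time and power output, which Aim 1c already names.
3. Report the CL1 and CL2 watts actually used before and after training, by group. Do not state that they were identical unless the records show it.
4. Use the constant loads only for the responses already listed as secondary: dyspnea, leg fatigue, deoxygenation, femoral blood flow and operating lung volumes. Replace the undefined constant-load parameters in Aim 1c accordingly.
5. Because 11 participants have already completed, date the change, label it as made after completion, and give the reason.

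The cost is wording in two sections, a short disclosure and a summary of ergometer settings. No new participants or visits are needed.
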